### 3 INTRODUCTION

#### 3.1 Background

#### 3.2 Coronavirus-19 (COVID-19)

Beginning in December 2019, Chinese scientists isolated a novel coronavirus, severe acute respiratory syndrome coronavirus 2 (SARS-CoV-2) from patients with virus-infected pneumonia which was later designated as coronavirus disease 2019 (COVID-19) by the World Health Organisation (WHO) (Zhou et al., 2020 [2]; Phelan et al., 2020 [3]).

Approximately 14% of those affected with this virus will develop severe disease requiring hospitalization and oxygen support; 5% will require admission to the intensive care unit (Handel et al., 2020 [4]). Severe cases may be complicated by acute respiratory disease syndrome (ARDS), sepsis and septic shock, and multi-organ failure, including acute kidney injury and cardiac injury. Risk factors for death include older age and co-morbid disease such as hypertension and diabetes (Zhou, et al., 2020 [2]).

#### 3.2.1 Coronavirus Biology

[figure not shown]
Coronaviruses, like other RNA-based viruses, do not have the machinery to synthesize their own nucleotides and thus depend upon the host intracellular pool of nucleotides for viral replication. In essence, viruses steal the host RNA building blocks, and without these building blocks they are unable to replicate. The SARS-CoV-2 is a single-stranded (positive sense) RNA virus with a genome that is 29,811 nucleotides long, quite a lot larger than other RNA-based viruses (e.g. the hepatitis C genome comprises only 9600 nucleotides). The nucleotide composition is broken down as: 29.9% adenosines, 18.4% cytosines, 19.6% guanines, and 32.1% uridines (Sah et al., 2020 [12]).

#### 3.3 Host Nucleotide Synthesis

Host *de novo* pyrimidine synthesis generates uridine monophosphate (UMP) as the building block for all pyrimidine ribonucleotides and deoxyribonucleotides (Figure 3-1). There exists no salvage pathway for the synthesis of UMP, the fundamental building block of pyrimidines. Inhibition of enzymatic steps upstream of UMP (Figure 3-1) leads to a rapid and profound depletion of intracellular pyrimidines.

#### 3.4 Dihydroorotate dehydrogenase (DHODH)

The enzyme dihydroorotate dehydrogenase (DHODH) catalyzes the 4th step of *de novo* pyrimidine synthesis and inhibition of DHODH completely halts all pyrimidine production. As shown in Figure 3-1, DHODH is located on the inner mitochondrial membrane and transfers electrons between DHO and complex III of the electron-transport chain via the reduction of its ubiquinone (coenzyme Q10) cofactor.

**Figure 3-1.** DHODH is a mitochondrial enzyme that catalyzes the 4th step of pyrimidine synthesis; it is completely essential for the generation of UMP.

DHODH is a clear therapeutic target for the inhibition of host pyrimidine synthesis. The chemical inhibition of DHODH *in vitro* or *in vivo* leads to the rapid depletion of UMP and subsequent depletion of downstream products thymine and cytosine. This forces a cell to rely on the salvage of extracellular pyrimidine nucleotides and this extracellular salvage is not capable of maintaining the cell's normal nucleotide pool (Sykes et al., 2016) [1]).

### 3.5 Brequinar

Brequinar is an orally available and potent inhibitor of DHODH. Brequinar is one of more than 300 quinoline-carboxylic acid derivatives prepared in an analog synthesis program in the 1980s, which was started after it was found that a compound of this class had antitumor activity. Brequinar was selected by DuPont for further development as a potential clinical drug because of its activity against experimental tumors and because its water solubility made it relatively straightforward to formulate.

In an indication such as treating SARS-CoV-2 infection, brequinar will act as a host-targeting antiviral. It is an orally available and potent inhibitor of dihydroorotate dehydrogenase (DHODH), the enzyme that catalyzes the fourth step in pyrimidine synthesis, namely the conversion of dihydroorotate (DHO) to orotate. DHODH inhibitors, including brequinar, inhibit *de novo* pyrimidine synthesis thereby leading to a depletion of a cell's pool of uridine, cytidine and thymidine ribonucleotides and deoxyribonucleotides.

The antiviral activity of brequinar has been demonstrated in studies of rotavirus replication in human intestinal Caco-2 cells as well as in human primary intestinal organoids (Chen et al., 2019 [6]). Treatment with teriflunomide, another DHODHi, has been effective *in vitro* and *in vivo* in a murine model of foot and mouth disease virus (Mei-Jian et al., 2019 [7]). DHODH inhibition (DHODHi) also inhibited the growth of dengue virus *in vitro* (Wang et al., 2011 [8]). DHODHi also showed antiviral effects against RNA viruses including influenza A, Zika, Ebola and coronavirus SARS-CoV-2 (Xiong et al., 2020 [11]). Brequinar has also been shown to inhibit the replication of Ebola virus, vesicular stomatitis virus and Zika virus *in vitro* (Luthra et al., 2018 [9]). Brequinar inhibits the replication of human immunodeficiency virus (HIV) *in vitro* (Andersen et al., 2019 [10]). When considering brequinar as an antiviral for treatment of SARS-CoV-2, oral brequinar is highly bioavailable (>95%) and has good penetration of lung tissue with an average tissue:blood ratio of 0.5 following a single dose of brequinar in the rat. It is therefore expected to achieve a similar period of DHODH inhibition in lung tissue (Brequinar IB [5]).

### 3.6 Rationale for the Planned Trial

DHODH inhibition has been extensively studied as a potential therapeutic target in the treatment of RNA-based viruses. The inhibition of DHODH is effective in inhibiting viral replication in pre-clinical models involving many RNA-based viruses with nanomolar potency and a high selectivity index (see the Brequinar IB [5], Section 5). In these pre-clinical models, the benefit of DHODH inhibition can be reversed by the supplementation of exogenous nucleotides, confirming that the on-target effect of host pyrimidine depletion is key to the anti-viral activity.

The CRISIS trial will study standard of care (SOC) and SOC with 5 days of DHODH inhibition. Clear Creek Bio hypothesizes that a defined 5-day course of brequinar will inhibit the enzyme DHODH to a degree sufficient to result in the transient depletion of host pyrimidine nucleotides,

PROTOCOL NUMBER: CCB-CRISIS-01  
PROTOCOL VERSION FINAL DATE: 10SEPT2020

Page 20 of 58

thereby inhibiting viral replication. A recent publication demonstrated that inhibitors of DHODH could potentiate the activity of inhibitors of RNA-dependent RNA polymerase (RdRp) in the treatment of dengue virus, another single-stranded RNA virus similar to SARS-CoV-2 (Liu et al., 2020 [13]). This inhibition of viral replication may restore the balance in favor of the host immune system for the clearance of SARS-CoV-2.

Marketed DHODHi medications are available, including leflunomide or teriflunomide, however these are very weak inhibitors of DHODH with cellular potency ~500 times lower than brequinar. These low potency inhibitors of DHODH are not expected to have the ability to acutely lower the pool of intracellular pyrimidines to the degree that is required for decreasing the viral load associated with SARS-CoV-2 infection, making brequinar the better choice for acute SARS-CoV-2 infection.

### 3.6.1 Brequinar Dose Selection

Safety data from previous oncology clinical studies of brequinar with 5 days of consecutive daily dosing suggest that 5 days of daily doses of 100 mg p.o. will be safe and well tolerated. A dose of 100 mg achieves plasma concentrations of approximately 1 uM (0.4 ug/ml) that should result in sufficient suppression of nucleotide synthesis. When given over 5-days, these plasma concentrations are achieved on a daily basis without accumulation, also reassuring the safety of this regimen (see Brequinar IB [5]).

### 3.6.2 Risk/Benefit of Brequinar

As presented in the Brequinar IB [5], an extensive database exists with more than 800 cancer patients exposed to this compound for treatment of a variety of solid tumors at various treatment regimens, doses, and routes including a single dose, once weekly, twice weekly, single dose every 3 weeks, daily times 5 every 4 weeks, and daily times 21 days for multiple courses. Brequinar has also been utilized at lower doses than used in the cancer studies in psoriasis and organ transplant. The maximum intravenous dose given was 2,250 mg/m^2 every 3 weeks, and the maximum oral dose was 100 mg/m^2 daily for 21 days. While no DHODHi has been tested to date in the clinic for infection with SARS-CoV-2 and no brequinar safety information is available in treatment of this disease, DHODHi therapy in the context of trials for patients with cancer has the expected safety side-effects of mucositis and bone marrow suppression. However, the prior clinical experience in 39 subjects who received daily brequinar for 5 consecutive days at or lower than 100 mg/day show no mucositis and only 1 (2.6%) episode of mild thrombocytopenia. The 100 mg per day dose proposed for administration in this study should be safe and well tolerated.

The possible benefit in using brequinar to treat SARS-CoV-2 infection is the hypothesis that a 5-day period of brequinar dosing will suppress host *de novo* pyrimidine synthesis for this period thus decreasing viral load. As discussed above, inhibition of DHODH is expected to reduce the ability of the virus to replicate and it is for this reason that study CCB-CRISIS-01 will administer brequinar to patients with COVID-19.

### 3.7 Risks Associated with Participation in the Clinical Study

In studies utilizing the weekly schedule of administration of brequinar in patients with refractory solid tumors, reversible myelosuppression, in particular thrombocytopenia, and mucositis have

PROTOCOL NUMBER: CCB-CRISIS-01  
PROTOCOL VERSION FINAL DATE: 10SEPT2020

Page 21 of 58

been the primary dose-limiting toxicities. In addition, skin rash, nausea/vomiting, fatigue, and leukopenia have been dose-limiting in trials utilizing other schedules of brequinar administration. However, these effects were self-limiting, transient, required treatment in few cases, and resolved following discontinuation of dosing. These adverse effects have been associated with higher doses of brequinar given via the intravenous route and for longer durations than the 100 mg dose and 5-day regimen proposed for this study.

COVID-19 patients are at higher risk of complications and poor outcomes when their infection is combined with comorbidities including hypertension, diabetes, chronic kidney disease, chronic obstructive pulmonary disease (COPD) or asthma, cardiovascular disease (coronary artery disease or congestive heart failure), liver cirrhosis, age > 65, and BMI > 30 [15]. It is likely that participants in this protocol who are sick enough to be hospitalized will have at least one of these comorbidities.

A comprehensive safety monitoring plan will be utilized in this study to assess the ongoing safety and well-being of participants (see [Section 10.8](#)).

### **3.8 Possible Interactions with Concomitant Medical Treatments**

While not previously tested in patients with viral infections, brequinar has been administered to subjects taking a variety of concomitant medications that are typical in severely ill cancer patients. No formal interaction studies have been conducted for these medications, however, there have not been any reports of interactions with any medications during the clinical trials with more than 800 cancer patients. Brequinar has also been used concomitantly with antibiotics, antifungals and other critical care medications.

There is no experience with brequinar for treatment of SARS-CoV-2 and other severe viral infections and no formal interaction studies have been conducted.

#### **3.8.1 CYP Interactions**

No formal clinical drug-drug interaction studies have been performed for brequinar with medications commonly used in treating hematologic malignancies. The nonclinical studies performed to date have demonstrated there is no first-pass metabolism and there have been no apparent hepatotoxic effects in the clinical studies. Brequinar itself does not appear to be a substrate for metabolism by cytochrome P450 enzymes when tested under a variety of conditions. (See Brequinar IB [5]; nonclinical data on file with Clear Creek).

### **3.9 Steps to be Taken to Control or Mitigate Risks**

All subjects will be treated in the hospital setting by highly experienced infectious disease or other critical care specialists and other qualified staff familiar with the treatment of severe viral infections and their complications. Subjects will be followed for study purposes through at least Day 15 even if improved enough to be discharged from the hospital.

#### **Subjects in the Brequinar Treatment Group**

If the subject is in the brequinar treatment group and is being discharged prior to completing the study, ensure a hematology/chemistry sample is obtained prior to discharge on the day of discharge. The subject is to return to the research or out-patient facility for the Days 7 and 15 visits if able and permitted. If unable or not permitted to return to the research facility due to COVID-19 restrictions, the remaining visit activities except for the lab draw will be conducted by phone

PROTOCOL NUMBER: CCB-CRISIS-01  
PROTOCOL VERSION FINAL DATE: 10SEPT2020

Page 22 of 58

or other digital media. The lab draw will be performed by an outpatient laboratory at a designated facility. Lab draws for any outpatient visits for the Day 7 and 15 visits are limited to safety labs (hematology and chemistry). Additional outpatient laboratory or study visits are to be conducted as needed for follow up of adverse events including hematologic toxicities.

PROTOCOL NUMBER: CCB-CRISIS-01  
PROTOCOL VERSION FINAL DATE: 10SEPT2020

Page 23 of 58

## **4 TRIAL OBJECTIVES**

### **4.1 Primary Objective**

- To determine the safety and tolerability of standard of care (SOC) and SOC plus brequinar in hospitalized COVID-19 subjects.

### **4.2 Secondary Objectives**

The secondary objectives of this study are:

- To determine the changes in clinical status measures listed through Day 15:
  - Hospitalization status
  - Duration of hospitalization
  - National Early Warning System 2 Score (NEWS2) Score
- To determine survival status through Day 29

### **4.3 EXPLORATORY OBJECTIVES**

- To determine the change in SARS-CoV-2 nasopharyngeal viral load through Day 15
- To determine the change in inflammatory markers through Day 15
- To determine the change in dihydroorotate dehydrogenase (DHO) through Day 15
- To determine the change in brequinar concentration levels through Day 7

PROTOCOL NUMBER: CCB-CRISIS-01  
PROTOCOL VERSION FINAL DATE: 10SEPT2020

Page 24 of 58

## 5 TRIAL DESIGN

This will be a phase 1a randomized, open label, multi-center study with approximately 24 subjects. All subjects will receive standard of care per institutional guidelines for treatment of patients with SARS-CoV-2 infection. In addition to standard of care, the brequinar group will receive brequinar 100 mg once daily for 5 days.

The Massachusetts General Hospital (MGH) COVID-19 Treatment Guidance is provided in [Appendix D Section 15.4](#). This guidance provides an example of standard of care instructions for treatment of COVID-19. The guidance is provided as informational only, it is not required that this guidance be used for treatment as standards of care may differ between institutions.

Subjects will have a Screening Visit followed as soon as possible with Study Day 1 (Day 1 may take place on the same day if entry criteria data are available). Study procedures are presented in detail in [Section 8](#). Subjects will be followed through Day 15, with mortality assessed via a phone call/other digital media acceptable to institution on Day 29.

If the subject is being discharged prior to Day 7, see [Section 8.5](#).

It is understood that some assessments may not be conducted if the subject is unable to return to the clinic after discharge due to restricted travel. If an assessment is missed due to after hospital discharge, e.g., samples or blood draws, this will not be counted as a protocol deviation. Any of the study visits may be conducted via telephone if the subject has been discharged from the hospital and is not permitted to or is unable to return to the hospital/clinic for these visits.

Information is to be collected using the electronic health record (EHR) whenever possible. It is not required to perform study-specific laboratory assessments, NEWS 2 assessments, etc. separately for study purposes.

PROTOCOL NUMBER: CCB-CRISIS-01  
PROTOCOL VERSION FINAL DATE: 10SEPT2020

Page 25 of 58

## **6 TRIAL ENDPOINTS**

### **6.1 Primary Endpoint**

- Safety/tolerability measured by rates of post randomization adverse events and hematology/chemistry safety labs.

### **6.2 Secondary Endpoints**

- Rates of/changes to the below clinical status measures through Day 15.
  - Hospitalization status
  - Duration of hospitalization in days
  - NEWS2 Assessments Days 1, 3, 5, 7, and Day 15 for hospitalized subjects.
- Mortality through Day 29

### **6.3 EXPLORATORY Endpoints**

- SARS-CoV-2 nasopharyngeal viral load: Day 1 (pre-dose), Days 3, 5, 7, and 15
- Inflammatory markers (to be specified in the Laboratory Manual, may include but are not limited to erythrocyte sedimentation rate (ESR), c-reactive protein (CRP), D-dimer, serum ferritin, and fibrinogen, procalcitonin, IL-6, IL-5, IL-2, IFN- $\gamma$ , final list to be determined) on Day 1 pre-dose, D3, D5, D7, D15 or at frequency per institutional standard of care. The markers are to be tested locally when possible; requested tests as listed in the Laboratory Manual that are not analyzed locally are to be shipped to the central laboratory for analysis.
- DHO concentration levels through Day 15.
- Brequinar concentration levels through Day 7

## 7 TRIAL POPULATION

### 7.1 Number of Subjects

Subjects who meet all the inclusion and none of the exclusion criteria will be enrolled in the study until approximately 24 subjects have completed the study. Subjects will be randomized to either standard of care or standard of care plus brequinar or in a 1:2: ratio (approximately 8 subjects assigned to standard of care alone and approximately 16 subjects on standard of care plus brequinar).

### 7.2 Inclusion criteria

1. Willing and able to provide informed consent for the trial, written, electronic, verbal or other method deemed acceptable by the institution and IRB.
2. 18 years of age or older.
3. If discharged from the hospital prior to Study Day 15 or if follow up is needed for study drug-related adverse event, willing to go to an outpatient facility if feasible or be in contact with the study team (phone call or other digital media) for remaining study assessments.
4. Laboratory-confirmed SARS-CoV-2 infection as determined by real time polymerase chain reaction (RT-PCR) or other Food and Drug Administration (FDA)-cleared commercial or public health assay.
5. Hospitalized (in patient with expected duration  $\geq$  24 hours)
6. The effects of brequinar on the developing human fetus are unknown. For this reason, women of child-bearing potential and men must agree to use adequate contraception (hormonal or barrier method of birth control; abstinence) prior to study entry and for the duration of study participation. Should a woman become pregnant or suspect she is pregnant while she or her partner is participating in this study, she should inform her treating physician immediately. Men and women treated or enrolled on this protocol must also agree to use adequate contraception for the duration of study participation and for 90 days after completion of brequinar administration.
7. Male subjects must agree to refrain from sperm donation from initial study drug administration until 90 days after the last dose of brequinar.
8.  $\leq$  10 days since first COVID-19 symptom as determined by treating clinician.
9. Able to swallow capsules.
10. At least one COVID-19 symptom including but not limited to fever, cough, sore throat, malaise, headache, muscle pain, gastrointestinal symptoms, shortness of breath, dyspnea, dysgeusia, or other symptom commonly associated with COVID-19. [22].

### 7.3 Exclusion Criteria

1. Any physical examination findings and/or history of any illness that, in the opinion of the study investigator, might confound the results of the study or pose an additional risk to the patient.
2. Active malignancy other than squamous cell carcinoma; anticancer treatment such as chemotherapy or radiation therapy within the past month.

PROTOCOL NUMBER: CCB-CRISIS-01  
PROTOCOL VERSION FINAL DATE: 10SEPT2020

Page 27 of 58

3. Nursing women or women of childbearing potential (WOCBP) with a positive pregnancy test.
4. Treatment with another DHODH inhibitor (e.g., leflunomide or teriflunomide), tacrolimus, sirolimus.
5. Platelets  $\leq 150,000$  cell/mm^3.
6. Hemoglobin < 10 gm/dL
7. Absolute neutrophil count < 1500 cells/mm^3
8. Renal dysfunction, i.e., creatinine clearance < 30 mL/min
9. AST and/or ALT > 1.5 ULN, or total bilirubin > ULN
10. History of bleeding disorders or recent surgery in the six weeks preceding enrollment
11. Concomitant use of agents known to cause bone marrow suppression leading to thrombocytopenia
12. History of gastrointestinal ulcer, or history of gastrointestinal bleeding.
13. History of hepatitis B and/or C infection, active liver disease and/or cirrhosis.
14. Heart failure, current uncontrolled cardiovascular disease, including unstable angina, uncontrolled arrhythmias, major adverse cardiac event within 6 months (e.g. stroke, myocardial infarction, hospitalization due to heart failure, or revascularization procedure).
15. Life expectancy of < 5 days in the judgment of the treating clinician.
16. Evidence of critical illness defined by at least one of the following:
  - a. Respiratory failure requiring at least one of the following:
    - i. Endotracheal intubation and mechanical ventilation, noninvasive positive pressure ventilation, ECMO, or clinical diagnosis of respiratory failure (i.e., clinical need for one of the preceding therapies, but preceding therapies may not be able to be administered in setting of resource limitation)
    - ii. Shock (defined by systolic blood pressure < 90 mm Hg, or diastolic blood pressure < 60 mm Hg or requiring vasopressors)
  - b. Multi-organ dysfunction/failure. See [22].

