### 7.3 Exclusion Criteria

1. Any physical examination findings and/or history of any illness that, in the opinion of the study investigator, might confound the results of the study or pose an additional risk to the patient.
2. Active malignancy other than squamous cell carcinoma; anticancer treatment such as chemotherapy or radiation therapy within the past month.
3. Nursing women or women of childbearing potential (WOCBP) with a positive pregnancy test.
4. Treatment with another DHODH inhibitor (e.g., leflunomide or teriflunomide), tacrolimus, sirolimus.
5. Platelets  $\leq 150,000$  cell/mm^3.
6. Hemoglobin < 12 gm/dL
7. Absolute neutrophil count < 1500 cells/mm^3
8. Renal dysfunction, i.e., creatinine clearance < 30 mL/min
9. AST and/or ALT > 1.5 ULN, or total bilirubin > ULN
10. History of bleeding disorders or recent surgery in the six weeks preceding enrollment
11. Concomitant use of agents known to cause bone marrow suppression leading to thrombocytopenia
12. History of gastrointestinal ulcer, or history of gastrointestinal bleeding.
13. History of hepatitis B and/or C infection, active liver disease and/or cirrhosis.
14. Heart failure, current uncontrolled cardiovascular disease, including unstable angina, uncontrolled arrhythmias, major adverse cardiac event within 6 months (e.g. stroke, myocardial infarction, hospitalization due to heart failure, or revascularization procedure).
15. Baseline COVID-19 severity characterized as “Critical” based on the FDA Guidance “COVID-19: Developing Drugs and Biological Products for the Treatment or Prevention (<https://www.fda.gov/media/137926/download>). Evidence of critical illness defined by at least one of the following:
  - a. Respiratory failure based on resource utilization requiring at least one of the following:
    - i. Endotracheal intubation and mechanical ventilation, oxygen delivered by high-flow nasal cannula (heated, humidified oxygen delivered via reinforced nasal cannula at flow rates > 20 L/min with fraction of delivered oxygen  $\geq 0.5$ ), noninvasive positive pressure ventilation, ECMO, or clinical diagnosis of respiratory failure (i.e., clinical need for one of the preceding therapies, but preceding therapies may not be able to be administered in setting of resource limitation)
  - b. Shock (defined by systolic blood pressure < 90 mm Hg, or diastolic blood pressure < 60 mm Hg or requiring vasopressors)

PROTOCOL NUMBER: CCB-CRISIS-01  

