	
 
5. Platelets <math>\leq 150,000</math> cell/mm^3.
 
6. Hemoglobin < 10 gm/dL
 
7. Absolute neutrophil count < 1500 cells/mm^3
 
8. Renal dysfunction, i.e., creatinine clearance < 30 mL/min
 
9. AST and/or ALT > 1.5 ULN, or total bilirubin > ULN
 
10. History of bleeding disorders or recent surgery in the six weeks preceding enrollment
 
11. Concomitant use of agents known to cause bone marrow suppression leading to thrombocytopenia
 
12. History of gastrointestinal ulcer, or history of gastrointestinal bleeding.
 
13. History of hepatitis B and/or C infection, active liver disease and/or cirrhosis.
 
14. Heart failure, current uncontrolled cardiovascular disease, including unstable angina, uncontrolled arrhythmias, major adverse cardiac event within 6 months (e.g. stroke, myocardial infarction, hospitalization due to heart failure, or revascularization procedure).
 
15. Life expectancy of < 5 days in the judgment of the treating clinician.
 
16. Evidence of critical illness defined by at least one of the following:             
 
a. Respiratory failure requiring at least one of the following:                 
 
i. Endotracheal intubation and mechanical ventilation, noninvasive positive pressure ventilation, ECMO, or clinical diagnosis of respiratory failure (i.e., clinical need for one of the preceding therapies, but preceding therapies may not be able to be administered in setting of resource limitation)
 
ii. Shock (defined by systolic blood pressure < 90 mm Hg, or diastolic blood pressure < 60 mm Hg or requiring vasopressors)
 
 
 
b. Multi-organ dysfunction/failure.
 
 
 

Treatment
	
All subjects will receive standard of care (SOC) per institutional guidelines. Subjects will be randomly assigned to SOC alone or SOC plus brequinar 100 mg daily x 5 days.

Stopping Criteria
	
Individual Criteria:
 
 
• Participants who develop a Grade 3 symptomatic toxicity that is assessed by the investigator to be related to the study drug are to be permanently discontinued from study treatment.
 

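### Exclusion 16 numbers shock as a sub-item of respiratory failure, so read literally shock without respiratory failure or multi-organ dysfunction does not meet the critical-illness exclusion

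*Protocol*

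**What the plan says.** Section 7.3 of the current version (10SEPT2020) opens the criterion with "16. Evidence of critical illness defined by at least one of the following". Two lettered items follow:

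- "a. Respiratory failure requiring at least one of the following". Under it, sub-item i covers ventilatory support, ECMO or a clinical diagnosis of respiratory failure. Sub-item ii is "ii. Shock (defined by systolic blood pressure < 90 mm Hg, or diastolic blood pressure < 60 mm Hg or requiring vasopressors".
- The second lettered item is "b. Multi-organ dysfunction/failure. See [22", with its reference to the cited guidance.

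The synopsis of the same version carries the same outline, with shock again labelled "ii. Shock (defined by systolic blood pressure" under item a.

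Section 9.5 has staff check every inclusion and exclusion criterion at screening, and check again on Day 1 if that falls on a different date. The synopsis allows 1 to 8 sites.

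**The concern.** The list levels and the sense of the words pull apart. The parent sentence asks for any one of several signs of critical illness, and shock has its own complete definition, as a free-standing sign would. The numbering, however, makes shock a qualifier of respiratory failure. The joining sentence then says that respiratory failure requires shock, which has no workable meaning.

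This is an operative safety exclusion that staff must tick off before randomisation. A site that follows the numbering would find that a patient with shock alone does not meet exclusion 16. A site that reads through the numbering would exclude the same patient. At stake is whether such a patient can be randomised and dosed, and whether sites apply one rule in a trial of about 24 subjects whose primary endpoint is safety.

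**Working it through.** No figure in the plan needs reproducing, because the question is one of logic. I wrote the criterion as a Boolean expression and compared the two ways of placing shock.

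**Inputs, all from exclusion 16 in Section 7.3:** R = respiratory failure (item a); V = the supports and diagnosis in sub-item i; S = shock (sub-item ii); M = multi-organ dysfunction or failure (item b).

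**As numbered:** excluded = [R and (V or S)] or M.

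**With shock level with a and b:** excluded = (R and V) or S or M.

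Without shock, both expressions reduce to (R and V) or M, so they agree. With shock present, the first reduces to R or M and the second is always true. They therefore differ in exactly one situation: shock present, respiratory failure absent, multi-organ dysfunction absent.

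| Shock | Respiratory failure | Multi-organ dysfunction | As numbered | Shock at its own level |
|---|---|---|---|---|
| yes | no | no | not excluded by 16 | excluded by 16 |
| yes | yes | no | excluded by 16 | excluded by 16 |
| yes | no | yes | excluded by 16 | excluded by 16 |

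**Is the nesting an artefact of text extraction?** No. The labels a, i, ii and b are explicit, and they agree between Section 7.3 and the synopsis.

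**Context from superseded text.** The file also holds earlier protocol versions. Those of 05JUNE, 06JULY and 31JULY2020 set shock level with respiratory failure; Section 7.3 of the 31JULY2020 version has "b. Shock (defined by systolic blood pressure < 90 mm Hg, or diastolic blood pressure < 60 mm Hg or requiring vasopressors". The nesting appears in the 05AUG2020 version and continues in the current one. A difference from superseded text is not itself an error, and the point rests on the current text alone. The history only makes a list-level slip a plausible explanation.

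**What else might stop the patient in the first row?** Other entry criteria in Sections 7.2 and 7.3 overlap with the gap:

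- Exclusion 1 applies to findings or illness that "in the opinion of the study investigator, might confound the results of the study or pose an additional risk to the patient". It is discretionary.
- Exclusions 8 (renal function) and 9 (liver tests) apply only if those values are abnormal.
- Exclusion 14 applies only to shock that accompanies the listed cardiac conditions.
- Exclusion 15 (short life expectancy) rests on clinical judgment.
- Inclusion 9 (able to swallow capsules) removes only those who cannot.
- Exclusion 16.b catches shock once several organs are failing.

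None of these applies the defined shock test itself.

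**The case against.** The strongest reply is that the harmful reading is the unnatural one. Because respiratory failure does not require shock, a clinician would probably take shock as a separate sign of critical illness and exclude the patient. If not, one of the other criteria might. Eligibility is settled before a randomised 1:2 allocation and the analyses are descriptive, so an unusual entrant adds noise to both arms and does not bias one against the other. On this view the matter is outline numbering.

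Much of that stands. The gap is limited to shock with no respiratory failure, no multi-organ dysfunction and no other bar to entry, at a site that follows the numbering. That sites would in fact differ is a possibility, not a documented event. A slip in editing cannot be proved from the text. But the reply asks staff to depart from the written numbering, in a criterion that they must confirm as written, and it leaves a defined safety exclusion to individual interpretation.

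A reader might infer more than the documents support:

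- **That investigator opinion is the only remaining safeguard, or that every patient with isolated shock would be admitted.** The other criteria listed above contradict both.
- **That such patients would inflate the study-level stopping counts of 4 and 8.** Section 8.4.2 counts only subjects on the brequinar arm, so a standard-of-care subject adds nothing. Under Section 10, conditions present before consent are medical history, and only a later change in severity becomes an adverse event. The shock definition can also be met by a diastolic reading alone, and nothing in the protocol shows that Grade 3 or 4 events would be likely in that group.
- **That the weight of one subject measures the problem.** One of 16 is 1/16 = 6.3% and one of 8 is 1/8 = 12.5%, but that is true of any subject in this trial and says nothing about how often the gap would operate.

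**Conclusion.** The point holds on the current text. In both Section 7.3 and the synopsis, exclusion 16 as numbered does not exclude a patient with shock who lacks respiratory failure and multi-organ dysfunction, and the sentence that produces this result does not make sense.

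The size in practice is unknown. The documents give no frequency for such patients, and several partial or discretionary criteria would remove some of them. The number who could enter through the gap may be small, and no effect on the stopping rule or on the comparison of arms has been shown. The conclusion assumes only that the letters and numerals in the list carry their ordinary meaning. It takes no view on what the clinical rule should be. The correction should be made because this is a safety exclusion that is applied literally and is cheap to clarify.

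**What to change.** The sponsor should confirm at which list level shock is intended to stand in exclusion 16. The outline in Section 7.3 and in the synopsis should then be reconciled with the opening sentence of that exclusion, so that the numbering and the wording state the same rule and every site applies it alike. The blood pressure limits and the vasopressor condition stay as they are. The cost is renumbering two lists in the next amendment, with a short note to sites if enrolment is under way.
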